7.7.2 Analysis of Secondary Effectiveness Endpoint

Descriptive statistics will be provided on the following endpoints in the PP analysis set in the Variable Flow study.

• Acute Procedural Success: confirmation of entrance block in all PVs.

The number and percentage of subjects with acute procedural success and the corresponding 97.5% exact binomial lower confidence bound will be presented.

• PV Isolation/ Acute Reconnection/ Touch-Up Application:

• PV isolation at the end of the procedure

Percent of subjects and percent of targeted PVs where PVI was achieved at the end of the index procedure, including additional RF application for the PV reconnection if applicable, will be summarized descriptively.

The achievement of PVI at the end of the procedure will be identified at the following time points, including 1) before the required 20-min waiting period, or 2) after the adenosine challenge was performed, and 3) after additional RF application for PV reconnection, whichever occurs last during the index procedure.

• Rate of PVI achieved at the end of procedure among targeted veins:

= number of targeted veins reaching PVI at the end of procedure total number of targeted veins

• Rate of PVI achieved at the end of procedure among subject:

= number of subjects reaching PVI at the end of procedure total number of subjects undergone ablation procedure

• PV isolation using QMODE+ as only ablation strategy

Percent of subjects and percent of targeted PVs where PVI was achieved at the end of the index procedure by using only the QMODE+ during the procedure will be summarized descriptively.

• Rate of PVI achieved by using QMODE+ only among targeted veins:

= number of targeted veins reaching PVI at the end of procedure by using QMODE + only total number of targeted veins

• Rate of PVI achieved by using QMODE+ only among subjects:

= $\frac{number \ of \ subjects \ reaching \ PVI \ at the \ end \ of \ procedure \ by \ using \ QMODE \ + \ only}{total \ number \ of \ subjects \ who \ underwentablation \ procedure}$

• PVs isolation after first encirclement (evaluated prior to the 20-minute waiting period and adenosine challenge)

Percent of subjects and percent of targeted PVs where PVI was achieved before the required 20-min waiting period, regardless the additional application was applied to remove the PV reconnection or not, will be summarized descriptively.

• Rate of PVI achieved prior to 20-min waiting period among targeted veins:

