= number of targeted veins reaching PVI prior to 20 – min waiting period total number of targeted veins

• Rate of PVI achieved prior to 20-min waiting period among subjects:

number of subjects reaching PVI prior to 20 – min waiting period total number of subjects who underwent ablation procedure

• PV isolation after first encirclement without acute reconnection (evaluated after waiting period and adenosine challenge)

Percent of subjects and percent of targeted PVs where PVI was achieved after the adenosine challenge and with no additional RF applications to remove PV reconnection will be summarized descriptively.

• Rate of PVI achieved after adenosine challenge among targeted veins:

 $number\ of\ targeted\ veins\ reaching\ PVI\ after\ adnosine\ challenge\ and\ without\ acute\ reconnection$

• Rate of PVI achieved after adenosine challenge among subject:

= number of subjects reaching PVI after adenosine challenge and without acute reconnection total number of subjects who underwentblation procedure

o Acute PV reconnection after first encirclement

Percent of subjects and percent of targeted PVs where PV reconnection was observed after the adenosine challenge will be summarized descriptively.

• Rate of acute PV reconnection among targeted veins:

= number of targeted veins with PV reconnection after adenosine challenge total number of targeted veins

Rate of acute PV reconnection among subject:

= number of subjects with PV reconnection after adenosine challenge total number of subjects who underwent ablation procedure

• PVs with touch-up (i.e. touch-up or ablation for acute reconnection)

Percent of subjects and percent of targeted PVs where additional RF applications was applied to remove PV reconnection, regardless the timing of PVI or the confirmation of the entrance block, will be summarized descriptively.

Rate of PV touch-up among targeted veins:

 $= \frac{number of targeted veins with touch - up RF application}{total number of subjects who underwent ablation procedure}$

• Rate of PV touch-up among subjects:

 $= \frac{number of subjects with touch - up RF application}{total number of subjects who underwent ablation procedure}$

• Repeat ablation procedures during 12-month period post procedure

• Rate of repeat procedures

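### Variable Flow SAP 7.7.2: the vein-level touch-up rate divides veins by subjects, so it overstates the rate by a factor equal to the mean number of targeted veins per subject

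*SAP*

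**What the plan says.** The measure is in SAP Section 7.7.2, in the item on PVs with touch-up. The introductory sentence promises two summaries, one per subject and one per vein: "Percent of subjects and percent of targeted PVs where additional RF applications was applied to remove PV reconnection". The first formula carries the label "Rate of PV touch-up among targeted veins" and reads "number of targeted veins with touch - up RF application}{total number of subjects who underwent ablation procedure" (the braces mark the fraction bar in the extracted text). The second, for subjects, reads "number of subjects with touch - up RF application}{total number of subjects who underwent ablation procedure". The two denominators are identical.

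The protocol defines the endpoint in the summary (Section 4.0, secondary effectiveness endpoints) and again in Section 8.2.3.2. Both places give a percentage of subjects and a percentage of PVs, with all targeted veins as the base. Protocol Section 18.9.5 leaves the analysis details for secondary endpoints to the SAP, so the SAP formula is what a programmer would follow.

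**The concern.** A rate among veins needs veins in the denominator. Veins over subjects gives a mean count per subject, which is not a percentage of veins and has no upper limit of 100%.

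Programmed literally, the formula would cause three problems in the tables:

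- The touch-up figure would be on a different scale from the vein-level acute reconnection rate defined just above it. If exactly the reconnected veins were touched up, at a true 20% and four veins per subject, the tables would show 20% reconnection beside 80% touch-up.
- The figure could never be lower than the subject-level touch-up rate, although the correct vein-level rate is normally the lower of the two.
- Below 100%, nothing in the number itself would reveal the error.

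If a programmer corrects it silently, the reported analysis departs from the prespecified formula.

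**Working it through.** **1. Compare the vein-level formulas for the index procedure in SAP 7.7.2.**

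| Measure | Formula as extracted | Denominator |
|---|---|---|
| PVI at end of procedure | "number of targeted veins reaching PVI at the end of procedure total number of targeted veins" | targeted veins |
| PVI with QMODE+ only | "number of targeted veins reaching PVI at the end of procedure by using QMODE + only total number of targeted veins" | targeted veins |
| PVI before the 20-minute wait (end of formula) | "min waiting period total number of targeted veins" | targeted veins |
| Acute reconnection | "number of targeted veins with PV reconnection after adenosine challenge total number of targeted veins" | targeted veins |
| PVI after adenosine challenge | denominator missing from extracted text | not usable |
| Touch-up | "number of targeted veins with touch - up RF application}{total number of subjects who underwent ablation procedure" | **subjects** |

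All four other formulas with a legible denominator use targeted veins. Touch-up alone does not.

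**2. Size of the error.** The plan states no figure for this endpoint, so there is none to reproduce. Let

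- T = targeted veins with touch-up
- V = all targeted veins
- S = subjects who underwent ablation
- k = V/S, the mean number of targeted veins per subject

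Then:

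- Rate as labelled: T/V
- Rate as written: T/S = (T/V) × (V/S) = (T/V) × k

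The overstatement factor is exactly k. It does not depend on S, and the formula is right only if k = 1.

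**3. Illustration.** S = 92 is the planned enrolment (SAP Section 1), so it is an upper limit for the analysis set. The documents do not give k; 3 to 5 is an assumption. T is chosen to give a true rate near 20%.

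| k | V = 92k | T | True rate T/V | As written T/S |
|---|---|---|---|---|
| 3 | 276 | 55 | 55/276 = 19.9% | 55/92 = 59.8% |
| 4 | 368 | 74 | 74/368 = 20.1% | 74/92 = 80.4% |
| 5 | 460 | 92 | 92/460 = 20.0% | 92/92 = 100.0% |

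A true rate of 10% would become 30%, 40% or 50%.

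**4. When the figure passes 100%.** This needs T > S, that is T/V > 1/k: 33.3%, 25% or 20% at k = 3, 4 or 5. With 92 subjects, it means more than 92 touched-up veins out of 276, 368 or 460.

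**5. Order relative to the subject-level rate.** Let D = subjects with any touch-up.

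- Each such subject contributes at least one vein, so T ≥ D and T/S ≥ D/S always.
- If every subject has the same k, then T ≤ kD, so T/V ≤ D/S.

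Together: T/V ≤ D/S ≤ T/S. A hypothetical case with k = 4, T = 74 and D = 40 gives a subject rate of 40/92 = 43.5%, a true vein rate of 20.1% and an as-written rate of 80.4%. The vein rate moves from below the subject rate to above it.

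**The case against.** The strongest objection is that the PDF extraction may be at fault. Formulas in this section are visibly damaged: one has no denominator, others have words run together, and most fraction bars are gone. The two touch-up fractions are adjacent with identical denominators, so a duplicated line cannot be excluded from the text alone. Against that, the disputed fraction is complete, with both parts in place, and nothing specific points to a misread. The objection justifies checking the original page before editing, but it does not outweigh the text as it stands.

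A second objection is that the intended quantity is clear from the label, the introductory sentence and the protocol, so a programmer would probably raise a query, and a value above 100% would expose itself. That is fair, but a value below 100% would not. The only related background figure is acute PV reconnection of 15–22% (Protocol Section 6.1). If that is read as a vein-level rate, which the text does not say, and touch-up is similar, the as-written figure at k = 4 would be 60–88%: wrong, but not impossible on its face.

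Third, the reversal of order is not certain. If every touched-up subject has exactly one touched-up vein, the as-written rate merely equals the subject-level rate. The ordering of the correct rates also assumes equal k across subjects. The error can reverse the order; it need not.

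Finally, the consequences are limited. SAP Section 7.7 makes secondary endpoints descriptive, Section 9 rests success on the primary endpoints, and Section 1 confines the Variable Flow results to additional claims. All of this stands. It limits the importance of the error without making the formula right. Nothing was found in either document that supports a per-subject denominator for this rate.

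**Conclusion.** The formula is wrong as written. It contradicts its own label, the sentence above it, the protocol endpoint and its four legible counterparts. Since the subject-level formula below it has the same denominator, correctly, a copying slip is the likely explanation. The algebra is exact; the illustrated sizes rest on the assumed 3 to 5 veins per subject and on assumed values of T and D. The conclusion is also subject to the original page matching the extracted text. Sample size, power, type I error, the primary endpoints, study success and the subject-level touch-up rate are not affected. It should be corrected because it is a prespecified instruction that would put a wrong percentage in the report.

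**What to change.** Check the formula on the original SAP page. If it reads as extracted, change the denominator of the vein-level touch-up rate to the total number of targeted veins, and leave the subject-level formula as it is. While on that page, confirm the denominator of the vein-level rate after adenosine challenge, which cannot be read in the extracted text.

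The cost is one denominator in the SAP. The count of targeted veins is already needed for the four other vein-level rates, and touch-up location and amount are already collected under Protocol Section 13.5. Nothing in the design or sample size changes.

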7.7.3 Analysis of Additional Endpoint

• Procedure Data

Procedural data such as total procedure time, PVI time, RF application time, mapping time, RF application time per lesion, total fluoroscopy time and dose, fluid delivered from the study catheter, location of RF applications, number of RF applications, repeat ablation rate, RF ablation parameters per application, device(s) utilized (per ablation), VISITAG[™] Settings, CF range, Power range will be summarized descriptively. These analyses will be conducted using the PP analysis set in the Variable Flow study.

• Quality of Life

AFEQT includes 20 questions on a 7-point Likert scale. Questions 1 - 18 evaluate Health Related Quality of Life (HRQoL) and Questions 19- 20 relate to patients' satisfaction with treatment^[1].

First 18 questions are also used to calculate Overall AFEQT score and subscale scores across three domains

- Symptoms: Four questions 1 4 assess AF related symptoms
- Daily Activities: Eight questions (5 12)
- Treatment Concerns: Six questions (13 18)

Overall and subscale scores range from 0 to 100. A score of 0 corresponds to complete disability, while a score of 100 corresponds to no disability.

Baseline values and changes from baseline at each time point the questionnaire is administered will be summarized descriptively for the following five scores. The overall AFEQT score and subscale scores across study visits will be plotted.

- Overall AFEQT Score (18 questions)
- Symptom Subscale Score (4 questions)
- Daily Activities Subscale Score (8 questions)
- Treatment Concern Subscale Score (6 questions)
- Treatment Satisfaction Score (2 questions)

These analyses will be conducted in the PP analysis set.

8 DATA MONITORING COMMITTEE- FOR INTERIM ANALYSIS

A Data Monitoring Committee (DMC) will be constituted to monitor subject safety. The DMC charter will document the constitution, roles and responsibilities of the committee, sponsor, and the independent statistician.

9 STUDY SUCCESS

The study will be considered successful if both primary endpoints are met.
